2.1. Study objectives

2.1.1. Primary objective

To evaluate the safety and tolerability of Chronocort® over time, as assessed by signs and symptoms of adrenal insufficiency or over-treatment, use of sick day rules, adrenal crisis, adverse events (AEs), laboratory measures and clinical observation.

2.1.2. Secondary objectives

The long-term efficacy of Chronocort® will be assessed over time by the measurement of:

- 1. Total daily dose of Chronocort® in milligram (mg)/day of hydrocortisone during the study and the incidence of dose titrations.
- 2. 17-OHP and A4, measured at two time points (at 09:00 and 13:00 hours) for:
 - a. Disease control at each visit as assessed by both 17-OHP and A4 levels in the optimal and normal range, respectively, at both time points.
 - b. 17-OHP and A4 standard deviation scores (SDS).
 - c. Change in absolute values compared to pre-Chronocort® baseline values.
- 3. Changes compared to pre-Chronocort® baseline in:
 - a. Bone turnover markers serum C-terminal cross-linked telopeptide (CTX), osteocalcin
 - b. Testosterone (total)
 - c. Fasting insulin and blood glucose levels, and glycated haemoglobin (HbA1c)
 - d. High sensitivity c-reactive protein (hsCRP) and plasma renin activity (PRA)
 - e. Body composition (dual energy X-ray absorptiometry [DEXA])(fat mass, lean mass, total bone density, T score and Z score) (except in Germany)
 - f. Quality of life (QoL) Medical Outcome Short Form (4-week recall) Health Survey Form 36 (Subject Questionnaire) (SF-36®), Multidimensional Assessment of Fatigue (MAF), EQ-5D™ Standardised Health Questionnaire (5-level) (EQ-5D™)

2.2. Study endpoints

2.2.1. Primary endpoints

The primary endpoint is the safety of Chronocort® over time, assessed using but not limited to the following endpoints:

- 1. Signs and symptoms of adrenal insufficiency or over-treatment throughout the study.
- 2. Use of sick day rules throughout the study.
- 3. Occurrence of adrenal crises throughout the study.
- 4. Occurrence of AEs throughout the study.
- 5. Change from pre-Chronocort® baseline in safety laboratory assessments at each visit throughout the study.
- 6. Change from pre-Chronocort® baseline in vital signs (blood pressure [BP], heart rate, respiration rate, body temperature), weight, body mass index (BMI), and waist circumference at each visit throughout the study.

2.2.2. Secondary endpoints

To assess the long-term efficacy of Chronocort®, the following secondary endpoints will be assessed:

- Total dose of Chronocort® in mg/day of hydrocortisone
- Disease control throughout the study as assessed by both 17-OHP and A4, in the optimal and normal range, respectively, at 09:00 and 13:00
- Change from pre-Chronocort® baseline at each visit in SDS of 17-OHP and A4 at 09:00, 13:00 and the mean of the two timepoints. Pre-Chronocort® baseline means prior to the first continuous dose of Chronocort® which is:
 - a. The reassessed baseline under DIUR-006 for subjects entering from study DIUR-003 and those subjects from DIUR-005 who had a gap between completing study DIUR-005 and starting study DIUR-006,
 - Visit 4 (week 24) from the feeder study for subjects who received standard glucocorticoid replacement therapy in study DIUR-005 and immediately entered DIUR-006,
 - c. Prior to the first Chronocort® dose in study DIUR-005 for subjects who received Chronocort® in study DIUR-005 (i.e. DIUR-005 baseline visit) and immediately entered DIUR-006
- Change from pre-Chronocort® baseline at each visit in the absolute values of 17-OHP and A4 at 09:00 and 13:00
- Change from pre-Chronocort® baseline at each visit in:
 - a. Bone turnover markers CTX, osteocalcin
 - b. Testosterone (total)
 - c. Fasting insulin and blood glucose levels, and HbA1c
 - d. hsCRP and PRA

e. Body composition (DEXA) (fat mass, lean mass, total bone density, T score and Z score) (except in Germany)

Protocol No.: DIUR-006

- f. QoL SF-36[®], MAF, EQ-5D™
- Incidence of dose titrations

2.3. Statistical hypotheses

Since all subjects participating in this trial will be receiving Chronocort®, there will be no formal treatment comparisons. Summaries over time will be produced for safety and efficacy parameters.

2.4. Exploratory objective and endpoint

2.4.1. Exploratory objective

To assess the relationship between disease control and the proportion of daily dose given at night.

To assess the relationship between total daily dose of Chronocort® per body surface area (mg/day/m²)

2.4.2. Exploratory endpoints

Disease control will be assessed by both 17-OHP and A4, in the optimal and normal range respectively. The proportion of daily dose given at night is the dose given at 23:00hrs divided by the total daily dose (sum of dose given at 07:00hrs and 23:00hrs).

The secondary endpoint of total dose of Chronocort® (mg/day) of hydrocortisone will be further described proportionally to patient body surface area (m²).

3. Study design

Subjects completing study DIUR-005 and those who have already completed study DIUR-003 will be offered the opportunity to either continue Chronocort® therapy or to switch from their current glucocorticoid therapy to Chronocort® in this open label extension study. An overview of the study plan is illustrated in Figure 1.

The intention is that subjects will transition straight from study DIUR-005 into DIUR-006 without a gap. However, during the conduct of the study, logistical issues arose precluding this for some subjects and so the protocol has been amended to allow these subjects who have been unable to transition immediately into DIUR-006 to be able to participate in the study (protocol amendment 6 incorporated into Protocol version 7.0 dated 21 June 2017). In general, subjects who complete study DIUR-005 should not have an interruption in treatment; if this does occur prior approval should be sought from the Sponsor before entering them into study DIUR-006.

All subjects will have a screening visit prior to the baseline assessment to allow DIUR-006 procedures to be fully explained and informed consent to be given by the subject. For subjects from DIUR-003 and any subjects from DIUR-005 who had a gap between completing study DIUR-005 and starting study DIUR-006 during which they received standard glucocorticoid therapy, this screening visit will include safety blood tests. Any subjects not meeting the inclusion/exclusion criteria following these blood tests will not be entered into the study.

All subjects will then return for the baseline visit. For subjects entering from study DIUR-003 and any subjects from DIUR-005 who had a gap between completing study DIUR-005 and starting study DIUR-006 during which they received standard glucocorticoid therapy, the full set of baseline

assessments will be completed, including 2 blood samples (one at 09:00 and one at 13:00 hours) for 17-OHP and A4 (note: baseline DEXA scan only needed for subjects entering from study DIUR-003). For subjects entering immediately from study DIUR-005 test results from their last visit in the feeder study (Visit 4) will be used for this baseline assessment, with the 09:00 and 13:00 hour results taken from the 24-hour hormone profiles conducted at the visit. Any subjects not meeting the inclusion/exclusion criteria following these blood tests will be withdrawn from this study (see section 9.3.2).

Once the baseline assessments are completed, the subjects will be given sufficient Chronocort® to use until Visit 2 (Week 4). Subjects entering immediately from study DIUR-005 who were previously on Chronocort® will continue on the same dose of Chronocort® as they were receiving at the end of the feeder study. Subjects from DIUR-005 on standard therapy, subjects from DIUR-005 who had a gap between completing study DIUR-005 and starting study DIUR-006 during which they received standard glucocorticoid therapy, and subjects from study DIUR-003 will have their initial dose of Chronocort® determined using the hydrocortisone equivalent of their previous treatment (immediately prior to the baseline visit. Note: conversion factors described in Section 9.2.3).

All subjects will return to the study centre at 4, 12 and 24 weeks after starting study DIUR-006 for additional blood tests and dose titration, if necessary. Dose adjustments will be decided by the investigating physician based on the "signs and symptoms of adrenal insufficiency questionnaire" and the measurement of 17-OHP and A4 (see CSP Section 8.1 for further detail). Subjects will receive a telephone call within two weeks of each visit to tell them the outcome of the dose adjustment process — either to tell them the new dose, or if no change in dose (which will also be followed up in writing). Visits thereafter will take place at 6-monthly intervals. However, if the investigator thinks that the Chronocort® dose needs to be changed at any point, then the subject should undergo a visit 4 weeks after the dose has been changed and the assessments specified for Week 4 (Visit 2) and the following telephone call should be conducted. The subject should then continue with the 6-monthly visit schedule as determined before this visit (i.e. the original timings will be maintained with this extra visit added in-between).

All subjects will receive telephone calls at 3 monthly intervals from Week 18, and unscheduled visits will be arranged if necessary. Subjects will also be provided with Chronocort® supplies from the study pharmacy at 3- or 6-monthly intervals.

[figure not shown]
Subjects who become pregnant whilst on-study must still be withdrawn from the study, however per protocol amendment 13 are allowed to re-enter the DIUR-006 study 6 weeks after the pregnancy is complete or 6 weeks after they finish breastfeeding (whichever is the later date). At the point of study re-entry, post-pregnancy subjects will have secondary baseline measurements taken for all the original baseline tests, including 2 blood samples (one at 09:00 and one at 13:00 hours) for 17-OHP and A4. Post-pregnancy subjects who re-enter will continue on their pre-determined visit scheduling based on the original baseline visit date, following completion of the mandatory secondary baseline visit and a Post Pregnancy Week 4 visit to enable the post-pregnancy dose levels to be checked.

The length of the study will be 5.5 years from the date of the first subject entering the study, so subjects will be treated for a maximum of 5.5 years.

Version: 6.0 12 July 2022

Figure 1: Overview of DIUR-006 Study Schema

Note: any subject who has a dose titration during the study will have a visit 4 weeks later Note: subjects with a gap between finishing study DIUR-005 and starting study DIUR-006 do not require an additional DEXA scan at the time they enter study DIUR-006

4. Timing of planned analyses

4.1. **Data Review Meeting**

The sponsor will convene a Data Review Meeting after the data has been cleaned and the database locked but before analysis has commenced. The review will be performed within the framework of the requirements of the ICH Guideline E9. The terms of reference for the Data Review Meeting are outlined in Section 13.8 of the protocol.

4.2. **Interim analyses**

Interim data analyses are expected to be required for regulatory review as part of any marketing authorisation applications. Prior to any interim data analyses a Data Review Meeting will take place as described in Section 4.1. No changes to overall study conduct are anticipated as a result.

4.3. Final analysis

The final analysis will take place after the Data Review Meeting described in Section 4.1.

5. Sample size considerations

Since this is an open label extension study to gather long term safety and efficacy data on Chronocort[®], no formal power or sample size calculations have been performed. All eligible subjects from study DIUR-003 (16 subjects) and DIUR-005 (120 subjects) may enter this study, giving a maximum of 136 subjects. Subjects from study DIUR-003 can be enrolled at any time (since this study has been completed), but subjects from study DIUR-005 will be enrolled when they complete Visit 4 of study DIUR-005. However, in some cases there may be a delay between a subject completing study DIUR-005 and starting study DIUR-006 during which the subject receives standard glucocorticoid therapy. In this case the subject should be entered into study DIUR-006 as soon as possible.

CONFIDENTIAL

6. Analysis populations

6.1. Full analysis set

The full analysis set comprises all subjects who entered the extension study and who subsequently received at least one dose of Chronocort[®]. All primary, secondary and exploratory endpoints will be summarised using the full analysis set. Subjects in the full analysis set will be analysed according to the actual treatment received.

6.2. Interim analysis set

The interim analysis set is a subset of the full analysis set. In addition to entering the study and receiving at least one dose of Chronocort®, subjects must have also completed the Week 24 (Visit 4) assessment or discontinued early from treatment and withdrawn from the study at the specified data cut-off requested for the interim analysis.

At the time of interim analyses all primary, secondary and exploratory endpoints will be summarised using the interim analysis set. Subjects in the interim analysis set will be analysed according to the actual treatment received. The interim analysis set will be used for all interim analyses carried out in this study.

7. Treatment comparisons

7.1. General

Since all subjects participating in this trial will be receiving Chronocort®, there will be no formal treatment comparisons. Summaries over time will be produced for safety and efficacy parameters.

For subjects who re-enter the study post-pregnancy, all data collected at following re-entry will be included in the summaries and analyses. For these patients, the original date of first dose of randomized treatment will be used as the date of origin for the assignment of visit windows and the calculation of relative date/time information.

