As soon as the pregnancy is confirmed, the Investigator will conduct as many of the evaluations included in the early withdrawal visit as possible (Section 11.1.10) and the subject will be asked to sign a pregnancy consent form to enable information on the course of the pregnancy to be collected. The Investigator will transition the subject from Chronocort onto standard of care therapy in line with the "DIUR-006 Participant Pregnancy: Advice to Investigators" document circulated to all Investigators in January 2020. AEs will be collected for 30 days after the early withdrawal visit and a follow-up telephone call will be conducted at 30 days, as detailed in Section 11.1.11. No other data will be collected while the subject is off study due to the pregnancy unless the Investigator considers any AEs are related to Chronocort treatment, in which case every reasonable attempt will be made to follow up until resolution of the event.

The outcome of the pregnancy will be collected via a Pregnancy Report Form that must be sent

If the subject decides to re-enter the study after the pregnancy, 2 post-pregnancy visits must be conducted:

- Post-pregnancy baseline visit, comprising the following:
  - o Re-consent for re-entry into the study.
  - Review of the inclusion/exclusion criteria to ensure the subject is still eligible for the study.
  - The tests detailed for the basline visit will be conducted (Section 11.1.2) to establish a new second post-pregnancy baseline (note: the androgen results will reflect the standard of care treatment only so the results will not be used to inform dose titration decisions)
  - The Chronocort dose used after re-entry should be determined using the hydrocortisone equivalent of the subject's standard of care dose at the end of the pregnancy/breast-feeding period. The first dose of Chronocort after re-entry should be taken in the evening of the first dosing day.
- Post-pregnancy Week 4 Visit (Section 11.1.3) and subsequent telephone call (Section 11.1.4)

On completion of the Post-pregnancy Week 4 Visit, subjects will attend their following study visits based on the schedule determined by their original baseline date (i.e. not using the new post-pregnancy baseline date).

Further details on data collection during pregnancy are provided in Section 12.12.

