#### 13 Statistical Considerations

A detailed and comprehensive statistical analysis plan (SAP) will be prepared and signed-off before the first subject has given informed consent for this extension study. Minor changes to the statistical methods set out in this protocol need not be recorded as a protocol amendment but must be documented in the SAP and in the study report.

Interim data analyses are expected to be required for regulatory review as part of any marketing authorisation applications. No changes to the overall study conduct and no changes to the planned formal statistical analyses are anticipated as a result.

Version: 20.0 – 16 Jun 2022 Page **49** of **96** 

The statistical analysis will be undertaken by The statistical analysis and report will conform to the relevant ICH requirements, including but not limited to those set out in ICH documents E3 and E9. SAS version 9.2 or later will be used for the analysis.

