#### 13.1 Conventions and Methods

#### 13.1.1 Summary Tables, Listings and Figures

The standard summary statistics for continuous baseline and outcome variables are: N, mean, standard deviation (SD), median, quartiles, minimum and maximum. The standard summary statistics for categorical baseline and outcome variables are: count and proportion (expressed as percentage). Geometric mean and coefficient of variation will also be presented for variables which will subsequently be log-transformed during the analysis.

Summary tables and figures will be supported by full subject listings.

Data will be summarised according to time since first dose of Chronocort® treatment (which may have been in the feeder study for study DIUR-005). Time slotting will be described in the SAP.

Safety and efficacy parameters will be explored based on previous treatment in the feeder study and by previous standard therapy. Exploratory analyses will also be undertaken to assess the relationship between disease control and the proportion of daily dose given at night. Further details will be provided in the SAP.

For subjects who re-enter the study post-pregnancy, data collected during the post-pregnancy phase will be listed only. Only data up to the time of first study withdrawal will be included in summary tables and figures. Individual subject profiles will be created to support discussion of data from this small subset of subjects in the clinical study report.

Disruptions due to the COVID-19 pandemic will be summarised by feeder study and previous treatment. The summary will include an overview of study visit or study medication disruptions due to the COVID-19 pandemic, as well as including whether the scheduled visit was delayed or scheduled assessments were not done. Detailed listings of study visit disruptions and study medication disruptions will be produced.

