The glucocorticoid therapies currently used often fail to normalise the growth and development of children with CAH. Also, adults may experience iatrogenic Cushing's syndrome, hyperandrogenism, infertility or the development of the metabolic syndrome (Arlt 2010). Chronocort®, a newlydeveloped modified release oral formulation of hydrocortisone, is designed to mimic the normal serum levels of the endogenous cortisol circadian rhythm, offering the prospect of an improved treatment outcome. Phase II and III studies have been carried out to evaluate whether a twice a day dosing regimen of Chronocort® given at night and in the morning (which can more closely normalise cortisol levels) will improve control of adrenal androgen production (as measured by 17-hydroxyprogesterone [17-OHP] and androstenedione [A4]). This study is a long-term extension study for subjects who were included in studies DIUR-003 and DIUR-005 to obtain long-term safety data and to continue to monitor long-term efficacy.

The proposed study aims to build on the results of studies DIUR-003 and DIUR-005 and evaluate the long-term safety of Chronocort® and also its long-term efficacy in improving control of serum

androgen levels (using 17-OHP and A4 as markers). The purpose of this document is to formally set out the primary and secondary analyses to be conducted for this study. SAP version 1.0 was written using protocol version 3.0 dated 26 July 2016. At the time of writing SAP version 2.0, the most recent version of the protocol is version 9.0 dated 08 November 2017. At the time of writing SAP version 3.0, the most recent version of the protocol is Version 11.0 dated 25 January 2019. At the time of writing SAP version 4.0, the most recent version of the protocol is version 14.0 dated 17 April 2020. At the time of writing SAP version 5.0, the most recent version of the protocol is version 15.0 dated 17 August 2020. At the time of writing SAP version 6.0, the most recent version of the protocol is version 20.0 dated 16 June 2022.

2. Study objectives and endpoints

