Individual question scores and GFI will be listed.

EQ-5D™

The EQ-5D™ questionnaire consists of two parts, the EQ-5D™ descriptive system and the EQ visual analogue scale (VAS). The descriptive system consists of 5 dimensions: mobility, self-care, usual activities, pain/discomfort and anxiety/depression. The EQ VAS is a visual scale in which the subject gives a single score between 0 and 100.

The results from the dimensions will be combined using a standard method specially designed for the EQ-5D™ questionnaire to give a single index value (EuroQol Research Foundation). Two methods will be used to calculate the single index value:

Method 1 will use the directly elicited 5L value set for the EQ-5D[™] questionnaire as specified in Devlin 2016.

Method 2 will use mapping approach described in van Hout 2012.

A table showing the frequency and percent of subjects with each score for each of the domains will be produced by previous treatment group, visit and feeder study. The denominator for percentage calculations will be based on the number of subjects with an evaluable EQ-5D, at each scheduled visit. A shift table of baseline to end of study will be produced by domain, previous treatment group and feeder study. The denominator for percentage calculations will be based on the number of subjects with an evaluable EQ-5D, at each level of the pre-Chronocort® baseline assessment.

The change from baseline and percentage change from baseline will be calculated for both the single index value calculated from the 5 dimensions and the VAS score. Summary statistics for the absolute values of these two scores as well as change and percentage change from baseline will be tabulated by previous treatment group, visit and feeder study.

Individual question scores for the EQ-5D™ descriptive system, the calculated single index value and EQ VAS score will be listed.

14. Changes from the planned analyses

Due to the COVID-19 pandemic, subjects in the US may receive domiciliary visits to take blood samples for analysis of their 17-OHP and A4 levels. These samples are scheduled to be taken at baseline, Week 4, Week 12, Week 24 and 6-monthly visits at both 09:00 and 13:00 hours, but these domiciliary visits will only occur once daily (with a preference for 09:00 hours). As a result, at the time of finalising the SAP there will unavoidably be missing data from what is due to be collected.

Statistical Analysis Plan

Version: 6.0 12 July 2022

15. References

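### Protocol 13.1.1 keeps data after post-pregnancy re-entry out of the tables, SAP 7.1 puts all of them in; under the SAP rule a sample taken on standard of care could be tabulated as a 6-monthly Chronocort result

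*SAP*

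**What the plan says.** **Protocol 13.1.1.** For subjects who re-enter after pregnancy, "data collected during the post-pregnancy phase will be listed only", and "Only data up to the time of first study withdrawal will be included in summary tables and figures". Individual profiles are to support discussion of these subjects in the study report.

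**SAP 7.1.** "For subjects who re-enter the study post-pregnancy, all data collected at following re-entry will be included in the summaries and analyses". It adds that visit windows and relative times for these subjects run from the original first dose, which it calls the first dose of randomized treatment.

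**Status of the two texts.** The SAP introduction says "At the time of writing SAP version 6.0, the most recent version of the protocol is version 20.0 dated 16 June 2022", so the SAP was not written against an older protocol. Protocol Section 13 says that minor changes to the statistical methods "need not be recorded as a protocol amendment but must be documented in the SAP and in the study report". SAP Section 14, on changes from the planned analyses, has one entry, which begins "Due to the COVID-19 pandemic, subjects in the US may receive domiciliary visits to take blood samples".

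**The re-entry visits.** Protocol 11.7 repeats the baseline tests at a post-pregnancy baseline visit and says that "the androgen results will reflect the standard of care treatment only". A post-pregnancy Week 4 visit follows, and then the original visit calendar resumes.

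**Visit windows.** SAP 9.3.1 summarises data by scheduled visit. It also says that if two or more visits, unscheduled ones included, fall in the same analysis window, the one closest to the target day is used, and the earlier one in a tie.

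**The concern.** Two current documents give opposite rules for the same records, so the choice would fall to whoever programs the tables. The choice affects content. The re-entry baseline is a pre-treatment sample on another therapy, but the SAP clock keeps running from the original first dose, so the sample lands on a study day that usually lies inside a 6-monthly window. Nothing in SAP 7.1 or 9.3.1 requires a windowed record to be on Chronocort. A 17-OHP or A4 value reflecting standard of care could then appear as that subject's Month 30 result, say, in tables meant to describe long-term control on Chronocort. The same rule decides whether AEs after re-entry appear in the tables that serve the primary safety objective.

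**Working it through.** **Inputs.** Table 7 of the SAP sets the window for Visits 5 to 14 at target ± 84 days. Visit 8 (Month 30) has target 913: 913 − 84 = 829 and 913 + 84 = 997, as printed. All thirteen printed ranges (Visits 2 to 14) reproduce from their half-widths.

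**Assumptions.**
- Windows reassign the re-entry visits, and the visit label does not block this.
- Re-entry day R is uniform over days 365 to 1825 (1461 days).
- The post-pregnancy Week 4 visit is on R + 28.
- Attended scheduled visits fall on their target days.

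A long gap means more than 168 days off study. A window spans 997 − 829 = 168 days from end to end, so no record from before withdrawal can share it.

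**One example.** R = 930 lies in the Visit 8 window, 930 − 913 = 17 days from target. Week 4 is day 958, which is 45 days from target. The next scheduled visit is day 1095. The standard-of-care sample is the closest record and becomes the Month 30 result.

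**Long gap, all re-entry days.** R lies in some 6-monthly window on 1353 of 1461 days (93%). How often it is the record used depends on whether a scheduled visit that falls due between re-entry and Week 4 is attended.
- *Not attended* (Protocol 11.7 resumes the calendar after Week 4): R is used from 14 days before target, where it ties with Week 4 and the earlier visit wins, to 84 days after. That is 99 days in a full window. Over the range: 85 + 7 × 99 + 15 = 793, and 793/1461 = 54%.
- *Attended:* R is used from target to 84 days after, 85 days in a full window. Over the range: 85 + 7 × 85 + 1 = 681, and 681/1461 = 47%.

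**What part comes from the closest-visit rule.** When R is 57 to 84 days after target, Week 4 falls outside the window and R is the only record in it. That is 28 days in each of 8 windows, or 224 days. There R is used only if windowing alone reassigns it. The closest-visit rule itself decides 793 − 224 = 569 days (39%) or 681 − 224 = 457 days (31%).

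**Short gap.** The shortest conceivable gap is 42 days, if the pregnancy ends at withdrawal. Scheduled visits from before withdrawal now compete. If the early withdrawal visit does not compete, R is used on 449 days (31%) or 337 days (23%) under the same two attendance assumptions. If it does, the figures are 281 days (19%) or 169 days (12%).

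**Under Protocol 13.1.1:** 0 days, because nothing after first withdrawal enters a table.

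**Time origin.** SAP 7.1 speaks of randomized treatment, but Protocol 10.1 says this study has no randomisation. SAP 9.3.1 counts from the DIUR-006 first dose on the evening of Visit 1. Protocol 13.1.1 counts from the first Chronocort dose, "which may have been in the feeder study for study DIUR-005", though it leaves time slotting to the SAP. A different origin would change which days are affected but would leave the conflict in place.

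**The case against.** The best counter-argument is that the visit-record problem may never arise. SAP 9.3.1 says data are summarised by scheduled visit and introduces the Table 7 ranges to flag extreme deviations for the Data Review Meeting. SAP Section 3 gives the re-entry visit its own label, a secondary baseline visit, and it is not obviously an unscheduled visit. A programmer working by label would leave it out. This stands, and it makes the consequence conditional. It does not remove it, because SAP 7.1 speaks of assigning visit windows for exactly these subjects and the closest-visit rule reaches beyond scheduled visits.

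It can also be said that SAP 7.1 documents the change by stating it, since Protocol Section 13 does not name SAP Section 14. That has some force, but SAP 7.1 does not say that it departs from the protocol, so a reader cannot tell a deliberate change from an oversight.

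The uniform range of re-entry days is artificial. The amendment history introduces re-entry only in April 2020, so early study days were out of reach. The window pattern repeats about every 182 days, so the shares move little.

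Three stronger readings are tempting and not supported:
- **Exposure is overstated.** Total duration in SAP 13.1 does span the absence, but it is defined as last minus first dose plus one and reported beside actual duration, which counts only days with a dose.
- **The shift tables are contaminated.** SAP 11.4 and 13.3 already limit the minimum and maximum to on-treatment values.
- **Tests not repeated at Week 4 (safety laboratory, vital signs, quality of life) are affected more often.** After a long gap, on every day counted for them, the re-entry baseline is the only record in the window, so the closest-visit rule never operates.

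**Conclusion.** The contradiction between Protocol 13.1.1 and SAP 7.1 is certain, and nothing in the available text reconciles it. That a standard-of-care sample could become a 6-monthly record is conditional on windows overriding visit labels. If they do, it would be the 17-OHP/A4 record on roughly 47% to 54% of possible re-entry days after a long gap and 12% to 31% after the shortest gap, under the assumptions listed. These are shares of days for a single re-entrant and do not measure bias in the results.

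A reader might infer that the overall efficacy picture is distorted. The documents do not support that: the study is descriptive with no formal comparisons, the protocol calls re-entrants a small subset, and their number is not given. The pooled effect is probably small. The point should still be settled before the final analysis, because the two rules produce different tables and correcting the text is cheap.

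**What to change.** Make the two documents state one rule before the final analysis. The sponsor should choose between:

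1. **Align SAP 7.1 with Protocol 13.1.1.** Tables and figures stop at first withdrawal; later data go to listings and subject profiles. This costs one SAP sentence. The price is that AEs after re-entry leave the tables, although the primary endpoint is AEs throughout the study.
2. **Keep some or all post-re-entry data in the summaries**, for example AEs only. The SAP's revision note for version 6.0 describes that middle course; it is a change log and nothing here rests on it. Amend the protocol sentence, or record the departure in SAP Section 14 and the study report. State in SAP 9.3.1 that the post-pregnancy baseline visit is excluded from the on-treatment visit windows. This costs a few sentences and minor programming.

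Under either option, replace the reference to randomized treatment in SAP 7.1 with the DIUR-006 first dose used in SAP 9.3.1. The duration definitions and shift tables need no change; at most, if post-re-entry data are summarised, add a footnote that total duration spans the absence.
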